3. STUDY DESIGN

3.1.1

Participants

99 stroke patients with dysphagia after an acute/subacute unilateral hemispheric infarction, presenting at Beth Israel Deaconess Medical Center (BIDMC) will be prospectively enrolled, if eligible, into the study. All stroke patients admitted to our hospital receive a standardized dysphagia screening using a bedside water swallow test and are referred for a swallow evaluation to a speech and language pathologist (SLP) if suspected of having dysphagia. Those with moderate to severe dysphagia (PAS ≥ 4) on a standardized videofluoroscopic swallowing (VFSS) evaluation will be invited for participation if they fulfill all study criteria. The patient as well as the SLP will be blinded to the stimulation allocation. Subjects will be randomly assigned to the two intervention or sham groups using PROC PLAN in SAS using a blocking scheme with block size of 6. Subjects will be stratified based on their baseline PAS score (4-6 vs. 7-8) before randomization to the three treatment groups.

3.1.2

Outcomes

Primary Efficacy Outcome: Penetration-Aspiration Score [PAS]: This is a validated 8 point ordinal scale that quantifies penetration and aspiration events observed during VFSS. Since aspiration after stroke is a major predictor of prolonged dysphagia and leads to dietary restrictions, increases the risk of pneumonia and need for tube feeding, this scale will be a relevant measure of swallow status. We have adopted a cut off PAS score ≥ 4 for study enrolment, as minor degrees of penetration can be seen in normal individuals. An average PAS score will be computed based on 5 swallows but if a specific bolus presentation is withheld due to safety concerns, the missing value will be replaced with the worst score (8) for that item.

Primary Safety Outcome: The major safety outcome measures will be **seizures, neurological and motor deterioration or stroke specific mortality** during the period of active stimulation. In light of our small sample size and low expected number of adverse events, we will rely on data from historical cohorts to derive our cut-off numbers for study suspension.

a. Seizures: We expect that a seizure provoked by tDCS would occur during the stimulation session and not thereafter. However, we will analyze the incidence of seizures during the 5 days of active stimulation since excitability changes from tDCS can be prolonged.

b. Neurological and Motor Deterioration: We will only include neurological deterioration not due to a new stroke, hemorrhagic transformation, or a coexisting encephalopathy. Deterioration will be defined as an increase in the NIHSS by ≥ 4 points between each successive day during active or sham stimulation. NIHSS score will be computed at the bedside by an investigator certified in its performance. Similarly motor deterioration for an individual patient is defined as a ≥ 2 point worsening from baseline on the NIHSS motor sub-item score for a given limb.

c. Swallowing Deterioration: We will record a FOIS score on day 3 of our protocol to assess any deterioration of swallowing with the allocated intervention (tDCS or sham). To minimize

radiation exposure VFSS will not be routinely used for this interim assessment. Subject with ≥ 3 point decrease in FOIS, will undergo an interim VFSS to obtain an interim PAS score. Swallowing deterioration will then be defined as an increase in the PAS score ≥ 2 points compared to baseline score based on this interim assessment not due to other confounding factors outlined above.

d. Stroke specific mortality: Deaths due to direct consequences of brain injury such as brain edema or seizure will count for stroke specific mortality, but not deaths from recurrent ischemic events, hemorrhage, pneumonia, cardiac events, and infections. All deaths will be reported to DSMB who will determine if the death is a possible consequence of tDCS or not.

e. Non serious events such as headaches, skin erythema, fatigue and visual perceptual changes will be tabulated to assess patient tolerability but will not be used as primary safety outcome measures due to their subjective nature. The seriousness of any unexpected adverse events such as a serious skin burn will be promptly reported to the DSMB

Secondary Outcomes: We will use 3 outcomes that assess swallowing physiology, 1 outcome that provides functional (dietary) measure of oral intake, and 3 major safety outcomes.

1. Outcomes of Swallowing Physiology:

a) Pharyngeal Constriction Ratio (PCR): PCR is a measure of the pharyngeal area visible in the lateral radiograph view at the point when a bolus is held in the oral cavity divided by the pharyngeal area at the point of maximum pharyngeal constriction during the swallow.

b) Hyoid, Laryngeal, and Pharyngeal excursion (HLPE): we will measure the actual excursion of these structures and landmarks from their resting point to maximal excursion. Hyoid, laryngeal and pharyngeal excursion are all important and semi-independent movements that close off the airway, shorten the pharynx, and open the upper esophageal sphincter, and thus are important variables to measure.

c) Pharyngeal Delay Time (PDT): will provide a temporal measure of the briskness of the swallow onset. We define PDT as “the time in centiseconds that the bolus is present in the hypopharynx before the swallow is triggered”. PDT will be measured from the time the bolus first passes the intersection of ramus of mandible and base of tongue, until the swallow begins - as seen by the final excursion of the hyoid bone associated with the swallow.

2. Dietary Outcome: Functional Oral Intake Scale [FOIS]: An important consequence of dysphagia is a compromised and altered diet. FOIS is a functional outcome that provides a validated measure of diet level. It has been tested and validated in stroke population and demonstrated to be sensitive to changes in swallowing functions in acute stroke patient. FOIS is an ordinal scale ranging from 1 (worst) to 7 (normal oral diet). It is easy to use and does not require specific training. It will be collected at four time points: 1) prior to initiating tDCS/sham stimulation (same day); 2) after the fifth session of tDCS/sham; 3) after the last session of tDCS/sham stimulation; and 4) by telephone at 1 month after the last stimulation session using a standardized questionnaire.

3.1.3

Protocol for Swallowing Evaluation

All participants will undergo 3 bedside swallowing evaluation and 2 standardized videofluoroscopic studies (VFSS) to further quantify dysphagia severity. The VFSS will be conducted by the SLPs at BIDMC according to established protocols. The first VFSS evaluation will occur on the day of first tDCS/sham stimulation session and the second evaluation will occur on the last (5th) day of stimulation. Prior to initiation of this project, the participating SLPs at BIDMC will undergo intensive training sessions with [name] (Boston University Medical Center) so that they can reliably detect deep penetration up to the vocal cords or aspiration (PAS score ≥ 4) on VFSS; patients will be enrolled if their PAS score ≥ 4 on at least one swallow. The SLP at BIDMC will not assign PAS scores which will be done by [name] team at their laboratory in Boston University Medical Center (BUMC). The de-identified and coded VFSS will be transferred electronically using a secure file transfer system on the same day to BUMC for detailed analysis and scoring. The lab at Boston University will be alerted immediately and will analyze the studies promptly to assess whether the PAS scores meet criteria for study enrolment. The patient will be viewed in the lateral plane for most swallows, but one swallow will be viewed in the anterior-posterior plane for asymmetry. The order of presentation will not be randomized but given in an incremental way due to the uncertainty about patient's swallowing status and for safety, as outlined below:

In Lateral view: One 5 ml Nectar Varibar Swallow, One 5ml Varibar pudding, 3 Varibar Thin Swallows: 5 ml thin liquids x1, 10 ml thin x 1, 30 ml thin x1;

10 ml & 30 ml thin liquids boluses are given only if no other boluses are aspirated

If a patient cannot take a bolus because of prior failures, a score of 8 will be automatically assigned to that bolus. This study will use a total of 3 bolus types and 5 swallows. The arithmetic mean of the PAS score will be computed for each patient, based on 5 swallows on lateral view. The PCR, PDT, and HLPE will be measured on the first trial of the 5 ml thin liquids swallows. These numbers of swallows can be tested in less than 5 minutes of radiation exposure time. All fluoroscopy studies will then be sent to BUMC to [name] laboratory, without patient identifiers, so that they are analyzed in a blinded fashion. Her research staffs, who are trained in this area, will record the following measures: (1) PAS (2) PCR, (3) HLPE, and (4) PDT. Inter-rater reliability of study analyses will be conducted for 30% of the studies, selected randomly. In addition, bedside swallow evaluation will be done on day 1 prior to initiating intervention, day 3 of intervention and after the final session and FOIS scores will be assigned for each assessment.

3.1.4

The Experiment Series and Stimulation Protocol

The experiments will be performed over 5 consecutive days for each subject. They will be blinded to their group allotment and will be unable to subjectively distinguish between tDCS versus sham stimulation. At the beginning of the study, besides the aforementioned swallowing evaluations and neurological assessments, information about handedness, biographical data, prior treatments, time of stroke onset (or last known time when subject was normal in those lacking a definite time of onset) and results of neuroimaging studies will be collected. TDCS will be delivered through a battery-driven, constant current stimulator (NeuroConn-DC Stimulator Plus). The area of electrode in contact with scalp will be 3 x 5 cm for the small electrode (anode) and 5 x 6 cm for the larger electrode (reference electrode).

A larger area for the reference electrode is chosen to enable current dispersion and minimize any possible biological effect at this site. For sham stimulation, the current will be ramped up to 2 mA and gradually decreased over 30 seconds, to produce a sensation of transient tingling, which is indistinguishable from active stimulation. This device has a “study” mode which allows for double blinding of both the operator and subject. In addition, the SLP involved in bedside swallowing evaluations and VFSS, as well as the investigator performing NIHSS will also remain blinded to the study allocation.

Electrode Placement: *Our aim is to stimulate the inferolateral regions of the primary sensorimotor and premotor cortex of the unaffected hemisphere.* We will use the international 10-20 EEG electrode placement system for this purpose as it has been shown to be accurate and used successfully to identify brain locations in other tDCS studies. We will place the anode mid-distance between C3/T3 [left] or C4/T4 [right] over the unaffected hemisphere and the reference electrode over the contralateral supraorbital region.

- **Stimulation Parameters:** We will use a current dose of 2mA for anodal tDCS. All subjects will undergo daily session of stimulation (tDCS or sham) for 5 consecutive days.

- **tDCS Device Programming and Fidelity Check:** Two individuals (device programmer) not involved in patient recruitment, stimulation sessions or outcome analysis will be assigned to program the tDCS device. They will receive the randomization code from the DCC and set the device to active or sham accordingly. For each treatment they will enter the subject ID and setting on a case report form (‘Blinded Information’ form, for the Data Center only). The programmer will deliver the device to the treating clinician, who after each treatment will return the device to the programmer. The programmer will verify that the device setting is correct and the device is working properly, and enter this information on the case report form.

- **Swallowing Exercises:** Patients will be given a lemon flavored lollipop to stimulate saliva production during these sessions. Food boluses or liquids will not be used because of a risk of aspiration and may add to the variability of swallowing effort. Each treatment session will consist of coaching the patient to perform an ‘effortful’ swallow, alternating with a ‘regular’ swallows. Prior to starting the sessions, the standardized “Effortful Swallow” maneuver will be taught and reviewed with patients by the SLP. Patients will be given simple verbal instructions such as: “When you swallow, press your tongue hard up to the roof of your mouth, then slide it back to the throat and squeeze your throat muscles and lift your larynx as high as possible.” In addition to the verbal instructions, we will use gesticulations to encourage aphasic patients to swallow at regular intervals. A laryngeal mic will be attached to the subject’s neck prior to each sessions and occurrence of a swallow response will assessed by the audio signal from the laryngeal mic as well as by observing the movement of the thyroid cartilage or by palpating its’ excursion in patients with thicker necks. A total of 40 effortful swallows will be attempted at every session. Patients complaining of dryness of mouth will be provided with 1-2 small ice chips from time to time. Each subject will have a separate binder with log sheets for each session. The number of swallows (0-40) performed by the subject at every session will be downloaded on a paper form and then sent to the DCC via RedCap. These sessions will be carried out in a patient room equipped with oxymeters and suction pumps so that in the remote event of an aspiration occurring, the material can be suctioned out promptly and other remedial measures are taken. [name] will train the

SLPs who administer effortful swallowing technique. Initial sessions will be videotaped or viewed in-person and evaluated by [name]; ad-hoc checks will be encouraged. [name] will retrain SLPs who do not follow the technique.

Intervention	Day 1	Day 2	Day 3	Day 4	Day 5	30 days
Sham group	Sham exercises +	Sham exercises +	Sham exercises +	Sham exercises +	Sham exercises +	
	Sham exercises +	Sham exercises +	Sham exercises +	Sham exercises +	Sham exercises +	
tDCS group (low-dose)	tDCS exercises +	tDCS exercises +	tDCS exercises +	tDCS exercises +	tDCS exercises +	
	Sham exercises +	Sham exercises +	Sham exercises +	Sham exercises +	Sham exercises +	
tDCS group (high-dose)	tDCS exercises +	tDCS exercises +	tDCS exercises +	tDCS exercises +	tDCS exercises +	
	tDCS exercises +	tDCS exercises +	tDCS exercises +	tDCS exercises +	tDCS exercises +	
Outcome Measures	PAS PCR, HLPE, PDT FOIS NIHSS	NIHSS	NIHSS FOIS	NIHSS	PAS PCR, HLPE, PDT FOIS NIHSS	FOIS

3.1.5

Neuroimaging Analysis

Computation of CBT-lesion load: We will perform functional imaging experiments in 8 healthy volunteers to identify the cortical swallowing centers and use this location as a seed region to identify the corticobulbar tract in a separate group of elderly healthy control subjects that had undergone high resolution DTI. The functional imaging experiment will consist of repeated swallowing trials contrasted with whole hand opening and closing tasks, done at the same frequency as the swallowing tasks. Functional MR images will be acquired with a gradient-echo T2*-weighted MR pulse sequence using our own modification of a sparse temporal sampling method with clustered volume acquisition to overcome imaging artifacts caused by swallowing motion. The voxel clusters of significant activation will be used as a seed region (to identify the cortical origin of the CBT). The second seed region will be defined in the posterior pons. The CBT will be traced from the cortical seed region in the swallowing cortex to the posterior pons regions. Exclusion masks will be drawn in order to exclude fiber projections that are not part of the CBT

Identifying and reconstructing the corticobulbar tract and determining the CBT-lesion load:

We will construct the corticobulbar tract by using the combination of fMRI activation patterns obtained and DTI in 12 healthy control subjects. The DTI scans will be high resolution studies obtained in normal controls, using a single-shot, spin-echo echoplanar imaging sequence with the following parameters: TR=10 seconds, TE=86.9 ms, resolution 2.6x 2.6 x 2.6 mm³, 30

noncollinear diffusion directions with a b value of 1000 s/mm^2 , and 6 acquisitions with a value of 0 s/mm^2 . Image acquisition, analysis, construction of corticobulbar tracts and computation of CBT-lesion load will be computed replicating methods described by Zhu et al (2010). The diffusion-weighted images of all acute patients will be normalized to a skull-stripped (using FSL BET at 0.5) T1-weighted SPM5 brain template with isotropic voxels $2 \times 2 \times 2 \text{ mm}$. This normalization is being chosen, since the T2-weighted Diffusion trace images tend to omit the skull and the T1 and the Trace image of the DWI have dark signal representing the CSF compartment.

Acquisition and Analysis of MRI Data: The MRI scans of all patients enrolled in the trial arm will be used for CBT-lesion load and infarct volume measurements. One experienced investigator who is blinded to subjects' behavioral outcomes will manually draw patient lesion masks. The drawings will be made using MRICro software (<http://www.mccauslandcenter.sc.edu/mricro>) on stroke patients' normalized Diffusion-Weighted Imaging studies. For the lesion load calculation, each stroke patient lesion map will be individually overlaid onto the canonical probabilistic CBT map to calculate the lesion load of each patient. Lesion overlap calculations for each patient were done as described by Zhu et al. (2010). In short, the maps will consist of voxel intensities ranging from $I = 0$ (voxel is not present in any part of the tract or functional gray matter map in any subjects) to $I = 12$ (the voxel is present in the part of the tract in all subjects). The probability of each voxel being a part of the tract is $1/12$ of that voxel's total intensity. Lesion load will be calculated by summing the total intersecting voxels between the lesion map and the voxel intensity from each probabilistic map.

3.1.6

Sample Size and Statistical Analysis:

Statistical Analyses: We will conduct two analyses: Intent to Treat (ITT) and Per-Protocol (PP) analyses. The primary analysis will be the ITT analysis.

Descriptive Analyses: For continuous variables, the mean, median, standard deviation, range, minimum, maximum, interquartile range, and sample size for each treatment group will be reported. For categorical variables the frequency distribution will be reported for each treatment group.

Baseline Comparability: While no substantial differences between treatment groups are anticipated given randomization, we will use summary statistics, graphical techniques such as boxplots, and univariate analyses to compare the baseline characteristics of treatment groups. Pre-treatment values will be compared between the placebo- and tDCS-groups using Analysis of CoVariance (ANCOVA) or the Mantel-Haenszel chi-squared test, as appropriate, to determine if the groups are balanced with respect to baseline characteristics while accounting for stratification by dysphagia severity. This comparison will allow us to identify potential confounders to be included in multivariate analyses.

Analytic plan Primary Aim. Primary analysis will use an intent-to-treat approach; thus all randomized subjects will be used in the primary analysis. For the primary outcome variable (PAS) a linear model will be fitted to the data using PROC MIXED in SAS. The outcome will be a change in mean PAS score. Treatment will be included as a categorical variable. Additionally baseline PAS and other variables that will be identified as confounders will be included as covariates. Adjusted means in the two tDCS groups will be compared to those in

the sham group. To control for multiple testing, we will employ the Hochberg-Benjamini procedure, which will result in positive study result if both null hypothesis are rejected at the 0.05 level or one is rejected at the 0.025 level. Similar analyses will be performed on the FOIS, PCR, HLPE, and PDT outcomes. To assess the durability of the intervention effects, a repeated measures analysis will be used. The outcome will be FOIS score at the onset of the trial and at 1 month. Treatment time and their interactions will be included as categorical variables. Additionally other variables that will be identified as confounders will be included as covariates. Adjusted means at the onset of trial and 1 month in the two tDCS groups will be compared to those in the sham group at each time point. *Safety analyses* will be run on all subjects receiving at least one round of intervention. The incidence rates of adverse events will be described as a whole and by treatment group. Adverse events will be presented with and without regard to causality based on the investigator's judgment. *Interim Analyses* No formal efficacy analysis will be performed. The study will not be stopped for early efficacy or futility.

Analytic plan for Secondary Aim: To assess the effect size across subject-specific predictors (baseline NIHSS score, dysarthria, CBT-lesion load and intubation), subgroup analyses will be conducted. For such analysis regression models will be employed that include intervention, covariate and covariate by treatment interactions as predictors and PAS scores, PCR, PDT, HLPE as outcomes, to examine the modifying effect of the covariates on the intervention. If a significant interaction is detected, analyses of major efficacy endpoints (PAS scores, PCR, PDT, HLPE) will be performed within each group.

Missing Data: Many longitudinal studies have the potential to suffer from problems with missing data. We anticipate a 35% - 40% attrition rate in this study, which includes drop-out, spontaneous recovery and discharge, based on review of our hospital records over the past 5 years. Based on experience, we do not expect any other serious problems with either the extent or the pattern of missing data but we will explore this issue by employing multiple imputation methods for handling missing data.

Sample Size and Power Calculations: We plan to enroll and randomize 99 subjects; 33 subjects to each of the two active and sham treatment. With the above sample size, after 40% attrition, we estimate that a difference of 1.0 and 1.15 standard deviations between the active and sham treatment in the mean primary outcome measure of the study can be detected with a type I error rate of 2.5% and power 80% and 90%, respectively. In our pilot study the difference we estimated was 1.35 with an approximate standard deviation for the differences in the two groups of 1.2, with a standardized difference of 1.1 standard deviations. Thus we expect to have $\geq 87\%$ power to detect the expected differences in our study. We also anticipate a greater effect size in the high dose group and thus the power to be greater.

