2. BACKGROUND AND STUDY AIMS

Dysphagia occurs frequently after a stroke and often leads to serious complications. Currently there are no effective therapies for improving swallowing functions in these patients. The usual clinical practice is to supplement nutrition using nasogastric or percutaneous gastrostomy tubes till swallowing improves spontaneously, if at all. These techniques however, do not prevent dysphagia complications like aspiration pneumonia; conversely, they may promote disuse of the swallowing mechanism, increase risk of gastrointestinal bleeding and worsen outcomes in some patients. Implementation of an intervention that improves swallowing in the early aftermath of a stroke can therefore be expected to improve patient outcomes and decrease costs of care.

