6.1.1. Evaluation of Safety

The DSMB will review demographic, baseline, treatment exposure, and safety data, including adverse events, serious adverse events, deteriorations and deaths, which will be

summarized prior to each meeting. Data to be reviewed will include tabulations of aggregate data (all data from all patients grouped), tabulations of unblinded comparative outcome data by treatment group, and by-patient listings.

In the role of safety advisory group for this study, the DSMB will:

- 1) evaluate the incidence of deaths, all adverse events, particularly serious adverse events and those reported with moderate or severe intensity, and other relevant measures of patient safety, patient enrollment and study completion status,
- 2) determine whether a modification or termination of the study is necessary to ensure patient safety or recommend continuing the study,
- 3) monitor the conduct of the study, e.g., rate of recruitment, ineligibility, non-compliance with the protocol, dropouts, and balance between treatments with respect to demographics,
- 4) inspect descriptive statistics of average PAS at baseline and Day 5 and of the change from baseline to Day 5,
- 5) inspect descriptive statistics of secondary outcomes (PCR, HLPE, PDT, FOIS, NIHSS) and change from baseline in secondary outcomes at each visit in which they are measured,
- 6) consider whether the trial or dose should be temporarily or permanently stopped based on pre-defined stopping rules for the number of certain type of adverse events. Specifically:
 - a. pause/stop enrollment in a dose if 3/10 or 4/20 in that dose exhibit seizures;
 - b. pause/stop all enrollment if at least 4/20 or 5/40 patients in both active doses combined experience seizure;
 - c. the mortality stopping rule will be the same as the seizure stopping rule; note that the probability for these rules is based on the following assumptions and on the binomial distribution:
 - i. we assume the natural history of the condition yields probability of seizure of 6% and probability of mortality of 7%;
 - ii. probability of stopping the study for safety, if these are the true probabilities, using the above stopping rules, is $\leq 5\%$;
 - iii. thus if a stopping rule is met, odds are that true rates are higher than 6%/7%;

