10. REPORTS PREPARED FOR THE DSMB

Data Presentations

The DCC will provide data as indicated below. The open session reports delivered to the Principal Investigator will not contain any treatment identifiers; whereas treatment will be discernible in the closed session reports distributed only to the DSMB.

Disposition, Demographics and Baseline

- Actual Enrollment vs. Projected Enrollment.
- Number of subjects screened, randomized, treated, and discontinued.
- Data compliance (% of missing forms based on the ratio of the number of data forms submitted vs. the number of data forms expected).
- Descriptive statistics of demographics and baseline characteristics, including baseline values of efficacy parameters.
- Incidence of inclusion/exclusion violations overall and by type of violation.

Treatment

- Number of subjects treated at each of Day 1 – Day 5.

Adverse Events and Deaths

- Number and percentage of subjects with treatment-emergent adverse events (TEAEs) overall and by AE type through 30 days post-dose (including neurological deterioration and swallowing deterioration).
- Number and percentage of subjects with treatment-emergent serious adverse events (TESAEs) overall and by AE type through study completion (including neurological deterioration and swallowing deterioration). (This will also be provided monthly via e-mail to the DSMB).
- Number and percentage of subjects with TEAEs overall and by AE type through 30 days post-dose, by maximum severity (including neurological deterioration and swallowing deterioration).
- Number and percentage of subjects with TESAEs overall and by AE type through study completion, by maximum severity (including neurological deterioration and swallowing deterioration).

- Number and percentage of subjects with TEAEs overall and by AE type through 30 days post-dose, by maximum relationship to study intervention (including neurological deterioration and swallowing deterioration).
- Number and percentage of subjects with TESAEs overall and by AE type through study completion, by maximum relationship to study intervention (including neurological deterioration and swallowing deterioration).
- Listing of serious adverse events (this will also be provided monthly via e-mail to the DSMB).
- Listing of deaths.
- Number and percentage of subjects with seizures, deaths, and swallowing, neurological and limb deteriorations.

Efficacy

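### Seizures after Day 5 and deaths from pneumonia, haemorrhage or infection cannot count toward the primary safety outcome, and the 6% and 7% reference rates state no window or death definition to match it

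*Combined protocol and SAP*

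**What the plan says.** **Window.** Section 3.1.2 (Primary Safety Outcome) restricts the major safety measures to events "during the period of active stimulation". For seizures it states that "we will analyze the incidence of seizures during the 5 days of active stimulation since excitability changes from tDCS can be prolonged". Neurological deterioration is an NIHSS rise "between each successive day during active or sham stimulation". The schedule in Section 3.1.4 has sessions on each of Days 1 to 5 and no NIHSS after Day 5.

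**Causes.** Item d of the same section counts deaths that follow directly from brain injury, "but not deaths from recurrent ischemic events, hemorrhage, pneumonia, cardiac events, and infections". Item b applies a similar filter: "We will only include neurological deterioration not due to a new stroke, hemorrhagic transformation, or a coexisting encephalopathy".

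**Reference rates.** Section 2 (Approach, B) says safety will be assessed by setting anticipated against observed incidence, and lists stroke specific mortality among the events. Section 3.1.2 says historical cohorts supply the cut-offs. Section 6.1.1, item 6(c), assumes "probability of seizure of 6% and probability of mortality of 7" per cent. It gives no period for either rate, and it speaks of mortality without the stroke-specific qualifier.

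**Other safety reporting.** Section 10 gives the DSMB treatment-emergent adverse events "overall and by AE type through 30 days post-dose", serious events through study completion, a listing of deaths, and counts of seizures, deaths and deteriorations. Section 3.1.6 describes adverse-event incidence by treatment group in the final analysis and names no window.

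**The concern.** The plan looks beyond the session for seizures because the effect on excitability may persist. That reason is honoured for Day 1, which has about four further days of observation, and hardly at all for Day 5.

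On mortality, Section 2 says of tube feeding that "These techniques however, do not prevent dysphagia complications like aspiration pneumonia", and Section 3.1.2 says aspiration raises the risk of pneumonia. If the intervention worsened swallowing, pneumonia would be an obvious fatal route, and those deaths do not enter the mortality component.

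The third gap is the comparator. An observed rate can be judged against an anticipated rate only if both cover the same period and the same events. If 7% describes all deaths over several weeks, a 5-day count of brain-injury deaths would tend to fall below it even without any benefit. Section 2 calls acute-phase safety data sparse and treats confirmation as a prerequisite for confirmatory trials, so the headline safety result is what later designers will rely on.

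**Working it through.** **1. The plan's own figure.** Section 6.1.1 says the seizure and mortality rules are met with probability at most 5% when the true rates are 6% and 7%. Exact binomial tails P(X ≥ r out of n):

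| Look | 6% (seizure) | 7% (mortality) |
|---|---|---|
| 3/10 | 1.9% | 2.8% |
| 4/20 | 2.9% | 4.7% |
| 5/40 | 9.0% | 14.5% |

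The first two looks agree with the stated limit one at a time; 5/40 does not. That is a separate matter, but it sets the false-alarm level for step 4.

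**2. The definitions side by side.**

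| Item | Period | Deaths counted |
|---|---|---|
| Primary safety outcome (3.1.2) | Days 1–5 | direct brain injury only |
| Reference rate 7% (6.1.1) | not stated | mortality, unqualified |
| DSMB count of seizures and deaths (10) | not stated | deaths, unqualified |
| TEAE tables (10) | to 30 days post-dose | not cause-restricted |
| Final safety analysis (3.1.6) | not stated | with and without regard to causality |

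Nothing in the documents links the first two rows.

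**3. How far a window mismatch could matter.** The period behind 6% and 7% is not given, so I assume it is W = 7, 14 or 30 days, with constant hazard. Then h = −ln(1 − p)/W, and the 5-day equivalent is 1 − exp(−5h). For 7% over 30 days: h = 0.07257/30 = 0.002419, and 1 − exp(−0.01210) = 1.2%.

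| Rate | W = 7 | W = 14 | W = 30 |
|---|---|---|---|
| 7%: 5-day equivalent | 5.1% | 2.6% | 1.2% |
| 6%: 5-day equivalent | 4.3% | 2.2% | 1.0% |

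Excluding causes of death would lower the mortality row further, by an amount the documents do not allow one to compute.

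**4. Illustration on the 5/40 look.** This applies only if the rule counts Day 1–5 events, which Section 6.1.1 does not say. Suppose treatment triples the hazard. The 5-day rate is 1 − exp(−15h). The rate over the whole reference window is 1 − (1 − p)³, which is 19.6% for p = 7% and 16.9% for p = 6%.

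| P(X ≥ 5 of 40), tripled hazard | W = 7 | W = 14 | W = 30 | Matched window, hazard tripled throughout |
|---|---|---|---|---|
| Mortality, 5-day count | 70% | 18% | 1.3% | 91% |
| Seizure, 5-day count | 57% | 11% | 0.7% | 83% |

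**5. Sensitivity to how long the harm lasts.** The last column assumes the raised hazard persists for all W days. If it is confined to Days 1–5 and W = 30, the 30-day rate is 1 − exp(−15h − 25h) = 1 − exp(−40h): 9.2% for mortality and 7.9% for seizure. A 30-day count then reaches 5/40 with probability 31% and 21%. With no treatment effect the figures are 14.5% and 9.0% (step 1). A longer window therefore gains much if harm is delayed, and less if it is not.

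**The case against.** The strongest reply is that the plan does look at later events. Every death goes to the DSMB for a judgement on whether stimulation could be responsible. The DSMB receives adverse events to 30 days, serious events to study completion and a listing of deaths, with comparative tabulations by group (Sections 6.1.1 and 10). The final analysis describes adverse events by arm with and without regard to causality. Worsened swallowing is followed directly by the Day 3 FOIS with a triggered VFSS, the Day 5 PAS and the one-month FOIS, and it has its own stopping rule. All of this stands. A reader might infer that delayed harm cannot be seen at all, or that pneumonia deaths are removed from the safety data. The documents do not support either reading: such events leave the primary outcome, not the record.

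The short window is also a reasoned choice. The plan expects a provoked seizure to occur during the session, and the sentence about prolonged excitability deliberately widens the window from the session to five days. It does not say that effects last for weeks. A narrow window favours attribution, and a wide one admits background events. This weighs against replacing the primary outcome, but not against reporting a second window beside it.

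Finally, the 5/40 calculation concerns a DSMB guideline rather than the primary outcome, and it rests on the two assumptions stated in steps 4 and 5. It therefore serves only as an illustration.

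**Conclusion.** The point holds as a matter of definition and comparability. Seizures after Day 5, and deaths from pneumonia, haemorrhage or infection, cannot count toward the primary safety outcome; they appear only in descriptive tables and DSMB review, and the final safety analysis has no stated window. Neurological decline after Day 5 can surface only as a reported adverse event, because no NIHSS is scheduled then. Separately, the anticipated mortality of 7% and the observed stroke specific mortality may measure different things.

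The documents do not fix the size. Under constant hazard, a 7% reference corresponds to a 5-day rate between 5.1% (7-day reference) and 1.2% (30-day reference). The 5/40 probabilities show direction only: they apply if the rules count Day 1–5 events and, for the 91% and 83%, if the raised hazard lasts the whole window. The headline safety result could look cleaner than the data, and a low-cost change prevents that.

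**What to change.** 1. In Section 3.1.2 and the safety analysis of Section 3.1.6, prespecify seizures and all-cause death from the first session through 30 days, by arm, as named safety outcomes. Show pneumonia deaths in the cause breakdown. Keep the 5-day and stroke-specific counts and report them alongside.
2. In Section 6.1.1, state the time window and death definition behind the 6% and 7%, and reconcile them with the events counted and with the stroke-specific definition in Section 3.1.2. No new boundary is proposed.

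The cost is mainly wording, since Section 10 already tabulates adverse events to 30 days post-dose and lists deaths. The one-month telephone contact is described only for FOIS, so the sponsor should confirm that seizures and vital status are ascertained then. The downside is that more background events unrelated to stimulation enter the count; the sham arm and the cause breakdown make these visible.
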